### **2.2.2.2 Efficacy**

- Time to clinical recovery up to Day 28
- Proportion of patients with clinical recovery up to Day 7, 14, 28
- Proportion of patients requiring supplemental oxygen up to Day 7, 14, 28
- Proportion of patients with intensive care unit transfer up to Day 7, 14, 28
- Proportion of mechanical ventilation up to Day 7, 14, 28
- Proportion of patients with all-cause mortality up to Day 14, 28
- Proportion of patients with hospital admission up to Day 14, 28

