10. EFFICACY ANALYSES

All Efficacy analysis will be conducted on the ITT set unless otherwise stated.

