10.1. SARS-CoV-2 Infection Symptom Checklist

All patients will be issued a patient diary for SARS-CoV-2 Infection Symptom Checklist at screening and will be required to record it in the diary from Day 1 until Clinical recovery or Day 28 whichever comes first. After Day 28, additional recording of the diary will be required if following conditions are met:

- For patients who will achieve clinical recovery at Day 28, patients will record the diary until Day 29 to confirm whether it is maintained at least 24 hours.
- For patients who will show deterioration (at the discretion of the Investigator) after the achievement of clinical recovery, patient will record the diary until secondary achievement of clinical recovery.
- After Day 28 of regular scheduled study visit, for patients with suspicious ADE occurrence, patient will record the diary for 7 days from the day of suspicious ADE occurrence specified in [Appendix 2](#).

All patients will be instructed to complete the diary twice a day in the following time point at approximately 12-hour intervals except for screening: In the morning (between 6 and 10 AM, approximately) and in the evening (between 6 and 10 PM, approximately). The patient will be recorded once at screening. On the date of study drug administration (Day 1), the patient diary

will be recorded twice before and after the study drug administration. If screening visit date and the administration of study drug date are same, the patient diary will be recorded twice before and after the study drug administration (Day 1).

SARS-CoV-2 Infection Symptom Checklist consists of 7 symptoms and the intensity of patient’s self-aware for each symptom. The 7 symptoms are feeling feverish, cough, shortness of breath or difficulty breathing, sore throat, body pain or muscle pain, fatigue, and headache. Scores for SARS-CoV-2 infection symptom are “Absent (0)”, “Mild (1)”, “Moderate (2)”, “Severe (3)” and “Not Done”.

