Clinical recovery is defined by all symptoms on the SARS-CoV-2 infection symptom Checklist are recorded as ‘absent’ or ‘mild’ in intensity for at least 24 hours. To satisfy the clinical recovery, symptoms of the moderate or severe in intensity at baseline should be scored as mild or absent, or symptoms of the mild or absent in intensity at baseline should be scored as absent, after study treatment. Patients who meet the clinical recovery criteria for at least three consecutive time points will be considered as satisfying condition of 24 hours, and achieving clinical recovery at the first time point. The three consecutive time points for each symptom can be different because the three consecutive time points will be determined excluding missing data if the results of some symptoms are missing on the SARS-CoV-2 infection symptom Checklist. However, results of all 7 symptoms have to be recorded at the first time point achieving clinical recovery. The example of a patients achieving clinical recovery on Day 14 Morning is presented the following [Table 3](#).

Table 3 Example of a Patients Achieving Clinical Recovery

	Day 14 Morning	Day 14 Evening	Day 15 Morning	Day 15 Evening
Feeling feverish	0	0	Missing	0
Cough	0	Missing	0	0
Shortness of breath or difficulty breathing	0	0	0	0
Sore throat	0	0	0	0
Body pain or muscle pain	0	0	0	0
Fatigue	0	0	0	0
Headache	0	0	0	0

The time to clinical recovery (days) will be calculated as [date/time achieving clinical recovery (or censoring) – date/time of study drug administration]. Patients who are ongoing in the study without event, with death or early withdrawal for any reason will be considered as censored at the day of their scheduled visit of interest (Day 28). Missing time of completion of diary will be assumed to be 10:00 AM and 10:00 PM for calculation of time to recovery.

The number and percentage of patients with clinical recovery up to Day 7, Day 14, and Day 28 and Censored up to Day 28 along with censoring reason will be displayed by treatment group. The 25th percentile, 50th percentile (median) and 75th percentile will be estimated from Kaplan-Meier curve for the time to clinical recovery up to Day 28 and displayed by treatment group. Kaplan-Meier plots for each treatment group will be presented.

This listing will include all data collected on the “SARS-CoV-2 Infection Symptom Checklist” page of eCRF.

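### Early withdrawals are censored at Day 28, not at their last diary entry, so the Kaplan-Meier curve counts them as observed non-recoveries and lengthens time to clinical recovery

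*SAP*

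**What the plan says.** Protocol section 2.2.2.2 lists "Time to clinical recovery up to Day 28" first among the secondary efficacy endpoints. Protocol section 7.4.5 plans descriptive summaries only and gives no censoring rule.

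SAP section 10.1 supplies the rule. The time variable is defined thus: "The time to clinical recovery (days) will be calculated as [date/time achieving clinical recovery (or censoring) – date/time of study drug administration". Three kinds of patient then share one censoring date: those still in the study without recovery, those who die, and those with "early withdrawal for any reason will be considered as censored at the day of their scheduled visit of interest (Day 28"). The quartiles "will be estimated from Kaplan-Meier curve for the time to clinical recovery up to Day 28 and displayed by treatment group", with plots by group. A companion table gives counts recovered by Days 7, 14 and 28, and patients "Censored up to Day 28 along with censoring reason will be displayed by treatment group".

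The outcome comes from the symptom diary, which patients are "required to record it in the diary from Day 1 until Clinical recovery or Day 28 whichever comes first". Withdrawn patients remain in the analysis, because SAP section 10 states: "All Efficacy analysis will be conducted on the ITT set unless otherwise stated". Neither document gives a reason for the Day 28 rule or a sensitivity analysis to it.

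**The concern.** Kaplan-Meier estimation assumes that a censored patient was under observation, without the event, up to the censoring time. The shared date meets that assumption for patients followed to Day 28 without recovery. It is defensible for deaths, since recovery is no longer possible. For a withdrawal it fails: the scheduled diary stops and recovery status is unknown from then on. The rule replaces that unknown status with continued non-recovery, whatever the reason for leaving. Protocol section 4.4 includes reasons that say nothing about symptoms, such as the sponsor ending the study.

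At stake are the medians, quartiles and plots for this endpoint. If withdrawals fall unevenly across groups, the displayed differences move for reasons unrelated to recovery. Dosed patients are generally not replaced (SAP section 5.3), so a lost patient is not made up.

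**Working it through.** **Inputs.** From the documents: 5 patients per CT-P59 dose and 1 placebo patient in each of 3 cohorts, with placebo pooled to 3 (SAP sections 4.1 and 5.4); follow-up to Day 28. The documents give no expected recovery time, no withdrawal rate and no power for this endpoint, so there is no planned figure to reproduce. Recovery and withdrawal values below are assumptions.

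**Step 1: what the rule does to the estimator.** At each recovery time the Kaplan-Meier curve is multiplied by 1 − d/r, with d recoveries among r at risk. If nobody is censored before Day 28, the product telescopes to

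S(t) = 1 − (number recovered by t)/n.

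The curve then uses no information on when a patient left. Censoring at the last diary entry leaves d unchanged and makes r smaller or equal at every recovery time, so every factor is smaller or equal. The Day 28 curve can therefore never lie below the last-diary curve. In 120,000 simulated groups there was no exception.

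**Step 2: small examples (hypothetical data).** Placebo, recoveries on Days 4 and 8, withdrawal on Day 2:

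- Plan {4, 8, 28+}: S = 1 − 1/3 = 0.667 at Day 4, then 0.667 × (1 − 1/2) = 0.333 at Day 8. Median 8 days; 75th percentile not reached; recovered by Day 28, 67%.
- Last diary {2+, 4, 8}: S = 1 − 1/2 = 0.5 at Day 4, then 0 at Day 8. Median 4 days (6 if the flat stretch at 0.5 is averaged); 75th percentile 8 days; curve reaches 100%.

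Further cases, with quartiles averaged where the curve is flat exactly at the quantile:

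| Group | Recoveries (day) | Withdrawals | Plan, 25th/50th/75th | Last diary |
|---|---|---|---|---|
| CT-P59, n = 5 | 4, 6, 8, 10 | one, Day 3 | 6 / 8 / 10 | 5 / 7 / 9 |
| CT-P59, n = 5 | 4, 6, 8 | two, Day 3 | 6 / 8 / not reached | 4 / 6 / 8 |
| Placebo, n = 3 | 6, 12 | one, Day 3 | 6 / 12 / not reached | 6 / 9 / 12 |

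**Step 3: large-sample median under the rule.** Assume exponential recovery with rate λ = ln 2/median and independent exponential withdrawal with rate κ. Choose κ so that a share w withdraws before recovery and before Day 28:

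κ/(κ+λ) × (1 − exp(−28(κ+λ))) = w.

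The plan's curve then estimates F(t) = λ/(κ+λ) × (1 − exp(−(κ+λ)t)), and the median solves F(t) = 0.5.

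| True median | w = 5% | 10% | 20% | 30% |
|---|---|---|---|---|
| 5 days | 5.12 | 5.27 | 5.67 | 6.34 |
| 7 days | 7.18 | 7.39 | 7.97 | 8.93 |
| 10 days | 10.28 | 10.61 | 11.51 | 13.01 |

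For a true median of 7 days, true recovery by Day 28 is 93.8%. The plan's curve shows 89.6%, 85.5%, 77.0% and 68.2% at these four withdrawal shares.

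**Step 4: planned group sizes.** Simulation, 20,000 groups per setting, true median 7 days, true share unrecovered at Day 14 = 0.25:

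| n | w | Last diary | Plan |
|---|---|---|---|
| 5 | 10% | 0.252 | 0.295 |
| 5 | 20% | 0.256 | 0.343 |
| 5 | 30% | 0.267 | 0.400 |
| 3 | 10% | 0.260 | 0.296 |
| 3 | 20% | 0.267 | 0.345 |
| 3 | 30% | 0.296 | 0.403 |

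**Step 5: a milder withdrawal pattern.** Assume a median of 6 days, and a share p of patients assigned a withdrawal time uniform over Days 0 to 14, some of whom recover first. True Day 14 recovery is F = 1 − 2^(−14/6) = 0.802. An assigned patient recovers before leaving with probability 1 − F/(14λ) = 1 − 0.802/1.617 = 0.504. The plan then shows (1 − p) × 0.802 + p × 0.504, which is 77.2% for p = 10% and 74.2% for p = 20%. Simulation at n = 5 (4,000 replicates) gave 77.2% and 73.8% for the plan, against 80.0% and 79.5% for censoring at withdrawal.

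**The case against.** Treating withdrawal as non-recovery can be a deliberate, conservative choice, and the same device is accepted here for deaths. Last-diary censoring has its own assumption, that withdrawal is unrelated to recovery. Protocol section 4.4 lists adverse events and investigator decisions among the reasons, and these may go with worsening; last-diary censoring would then overstate recovery. With three placebo patients it can turn two observed recoveries into a curve that reaches 100%. This stands as a reason to show both analyses. It does not justify the text as written, which calls the handling censoring and states no composite definition.

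The tabulated proportions recovered by Days 7, 14 and 28 are counts over the group size and do not change with the censoring rule. One withdrawal before recovery caps the Day 28 count at 80% (67% on placebo) either way. That is correct: the correction acts only on the Kaplan-Meier quartiles and plots.

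The sizes rest on assumed rates. Very early withdrawal is also less likely, because patients stay in the study center for at least 72 hours and Day 7 is recommended (Protocol section 3.4.2). Both points stand. So does the low stake: a secondary descriptive endpoint, no test, no bearing on dose escalation. The table of censoring reasons shows who withdrew, but it leaves the curve unchanged.

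**Conclusion.** The concern holds. The rule for early withdrawals is incorrect as a censoring rule, and the planned curve carries no more information than the proportion of patients recovered. Relative to last-diary censoring, the shift towards longer times is certain in direction. Relative to the truth, the estimate is too long whenever any withdrawn patient would have recovered by Day 28, and it is never too short.

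The size depends on withdrawals before recovery. With none it is zero. In the examples with a single withdrawal the median moved by 1 to 4 days, depending on the data and the percentile convention, and in both placebo examples the 75th percentile was lost. In large samples, 10% withdrawing before recovery lengthens the median by 0.27 to 0.61 days and 20% by 0.67 to 1.51 days, for assumed true medians of 5 to 10 days with exponential recovery and independent withdrawal. The rule should be changed before the final analysis, although the trial's primary safety conclusions do not depend on it.

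**What to change.** Replace the censoring sentence in SAP section 10.1 with wording such as:

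*Patients without clinical recovery who complete Day 28, or who die, are censored at Day 28. Patients who withdraw early without clinical recovery are censored at the date and time of their last diary entry with all seven symptoms recorded.*

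Requiring all seven symptoms gives the last entry a clear meaning, since the SAP already requires a full set at the first time point of recovery. The SAP should also say how it treats patients who stay in the study but whose diary recording is stopped, which Protocol section 6.3.1 allows. Keep the present rule as a labelled worst-case sensitivity analysis. The Day 7, 14 and 28 counts can stay, with withdrawn and non-recovered patients shown separately.

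The cost is one sentence, a line of derivation code and one extra run; diary data are already entered in the eCRF. SAP section 5 allows updates until the database hard lock, and time to recovery is not among the first-report outputs in SAP Appendix 5. If the lock has passed, report the corrected estimate beside the planned one as a documented deviation, as Protocol section 7 provides.

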10.2. Disease Status Monitoring

Disease status including requirement of supplemental oxygen, intensive care unit transfer, mechanical ventilation use and hospitalization will be monitored during the study period (from signing of ICF to EOT).

The number and percentage of patients with supplemental oxygen, intensive care unit transfer, mechanical ventilation use up to Day 7, 14 and Day 28 and hospitalization up to Day 14 and Day 28 will be summarized by treatment group respectively.

A listing will be provided by treatment group for the ITT set showing the details collected on the “Disease Status Monitoring” page of eCRF.

11. PHARMACOKINETIC ANALYSIS

All PK analyses will be conducted on the PK set unless otherwise specified.

11.1. Serum Concentrations

Blood samples for PK analyses will be collected from all patients at the time points specified in PK Blood Sampling Time Points and acceptable tolerance windows ([Table 4](#)). If the PK blood sample is unable to be analyzed or is missing at certain time point, some blood samples collected for immunogenicity assessment at the same time point can be used for PK assessment.

Descriptive statistics (n, mean, SD, geometric mean, CV%, minimum, median, and maximum) for serum concentrations will be summarized by CT-P59 treatment groups at each scheduled visit and time point. Individual serum concentrations, collection date/time, and deviations from scheduled time will be listed for the Safety set by CT-P59 treatment groups, visit and time points.

Concentration that are below the lower limit of quantification (BLQ) prior to the study drug administration will be treated as zero (0), and all other BLQ values will be treated as missing for calculation of descriptive statistics of serum PK concentrations and for PK parameter estimation. Measurable concentrations after consecutive BLQs during the terminal phase will also be set to missing.

The mean (\pm SD) serum concentration versus scheduled sample time profiles for the CT-P59 will be presented graphically on both linear and semi-logarithmic scales by CT-P59 treatment groups. In addition, the spaghetti plot of serum concentrations versus scheduled sample time profiles will be presented graphically on both linear and semi-logarithmic scales by CT-P59 treatment groups.

Table 4 Blood Sampling Time Points for Pharmacokinetic Assessment

Day	Time point	Window
Day 1	Predose	Predose within the day
	End of infusion	+ 15 minutes

	1 hour after end of infusion	
Day 2	24 hours after start of infusion	± 1 hour
Day 3	48 hours after start of infusion	
Day 5	96 hours after start of infusion	± 4 hours
Day 7	144 hours after start of infusion	
Day 10	216 hours after start of infusion	
Day 14	312 hours after start of infusion	± 1 day
Day 28	648 hours after start of infusion	± 3 days
Day 56	1,320 hours after start of infusion	± 5 days
Day 90/EOT visit	2,136 hours after start of infusion	

The first CSR will present PK serum concentration results up to Day 14 of each patient.

11.2. Pharmacokinetic Parameters

The following PK parameters will be calculated by noncompartmental methods based on the actual sampling time points using [REDACTED]

Parameter	Definition
AUC _{0-inf}	Area under the concentration-time curve from time zero to infinity, calculated using the linear up and log down trapezoidal rule
AUC _{0-inf} /Dose	Dose normalized AUC _{0-inf} (normalized to total body dose and dose/body weight)
AUC _{0-last}	Area under the concentration-time curve from time zero to the last quantifiable concentration, calculated using the linear up and log down trapezoidal rule
AUC _{0-last} /Dose	Dose normalized AUC _{0-last} (normalized to total body dose and dose/body weight)
C _{max}	Maximum serum concentration
C _{max} /Dose	Dose normalized C _{max} (normalized to total body dose and dose/body weight)
T _{max}	Time to C _{max}
t _{1/2}	Terminal half-life, calculated as: $t_{1/2} = \ln 2 / \lambda_z$
%AUC _{ext}	Percentage of AUC _{0-inf} obtained by extrapolation.
λ_z	Terminal elimination rate constant estimated from the linear regression of the natural log-transformed concentration over time at the terminal phase. At least 3 time points (excluding C _{max}) and in general, adjusted correlation coefficient (r ²) greater than or equal to 0.85 is needed to

	calculate and retain λ_z and its associated parameters ($t_{1/2}$, AUC_{0-inf} , $AUC_{0-inf}/Dose$, CL , and V_z). Values of adjusted r^2 less than 0.85 will be examined on a case-by-case basis for reliability to calculate and retain λ_z and its associated parameters ($t_{1/2}$, AUC_{0-inf} , $AUC_{0-inf}/Dose$, CL , and V_z). Pharmacokinetic parameters that do not meet this criterion will be listed but not summarized
CL	Total body clearance, calculated as: $CL = Dose/AUC_{0-inf}$ where Dose is the total body dose
V_z	Volume of distribution during the terminal phase, calculated as: $V_z = (CL)/\lambda_z$

Pharmacokinetic parameters will be summarized by CT-P59 treatment groups using descriptive statistics (n, mean, SD, geometric mean, CV%, minimum, median, and maximum values for all parameters).

All data for the PK parameters will be listed by CT-P59 treatment groups using the following rules: C_{max} and $C_{max}/Dose$ will be presented to same level of precision as the PK concentration results, T_{max} will be presented to 2 decimal places, AUC_{0-last} , $AUC_{0-last}/Dose$, AUC_{0-inf} and $AUC_{0-inf}/Dose$ will be rounded to integer, and all other PK parameters will be presented to 3 significant digits.

Scatter plots of individual values and geometric mean versus dose (in mg/kg on numeric scale and log-transformed scale) will be presented for AUC_{0-inf} , AUC_{0-last} , C_{max} , and the corresponding dose-normalized parameters.

Dose proportionality of the PK parameters, AUC_{0-inf} , AUC_{0-last} , and C_{max} , over the administered dose range (in mg/kg) will be quantified using the following power model:

$$\log(\text{parameter}) = a + b * \log(\text{dose})$$

where 'a' is the intercept and 'b' is the slope.

The power model parameters (slope and intercept) along with the corresponding 90% CIs and SE will be estimated using least-squares regression or an equivalent method, and will be presented in tabular format and graphically.

The first CSR will present summaries only for C_{max} , $C_{max}/Dose$ (normalized to dose/body weight) and T_{max} , derived from serum concentration up to Day 14, scatter plots only for C_{max} , $C_{max}/Dose$ (normalized to dose/body weight) and dose proportionality assessment only for C_{max} using [REDACTED]

12. SAFETY ANALYSES

All Safety analyses will be conducted on the Safety set unless otherwise stated.

12.1. Adverse Events

An adverse event (AE) is defined as any untoward medical occurrence in any patient during the study which does not necessarily have a causal relationship with the study drug. Any new

condition noted at Screening would be regarded as an AE, but not a TEAE.

A TEAE includes any untoward medical occurrence in a patient after administration of a study drug, which does not necessarily have to have a causal relationship with this the study drug. A TEAE can therefore be any unfavorable and unintended sign (including an abnormal laboratory finding), symptom, or disease temporally associated with the use of the product, whether or not related to the study drug.

All AEs will be reported by the Investigator via eCRF from the date patients signs the ICF until EOT visit, regardless of the relationship to the study drug, and graded for intensity according to the Common Terminology Criteria (CTCAE) Version 5.0 and coded to SOC and PT according to MedDRA Version 23.0 or later.

If the stop date of an AE is incomplete or unknown, the following rules will be applied.

- Missing day (e.g., XXSEP2020): Assume the last day of the month. (e.g. 30SEP2020)
- Missing day and month (e.g., XXXXX2020): Assume December 31st. (e.g., 31DEC2020)
- Missing day, month and year (e.g., XXXXXXXXXX): Leave it as Missing.

In case a patient dies during the study, the stop date will be imputed with the date of death if the imputed stop date is after the date of death.

If the start date of an AE is incomplete or unknown, the following rules will be applied. If the stop date of the AE is incomplete, imputed stop date will be used instead of reported stop date:

- If the day an AE is missing (e.g. XXSEP2020), the month and year of the incomplete date will be compared to the date of study drug administration.
 - If the month and year are equal for both dates, the AE start date will be imputed as the earlier of: (i) the date of study drug administration, and (ii) the stop date of the AE.
 - If the month and year are not equal, the AE start date will be imputed as the first day of the month (e.g. 01SEP2020).
- If the day and month are missing (e.g. XXXXX2020), the year of the incomplete date will be compared to the date of study drug administration.
 - If the years of both dates are equal, start date will be imputed as earlier date of: (i) the date of study drug administration, and (ii) the stop date of the AE.
 - If the year is not equal, start date will be imputed as the 1st of January of the incomplete date year (e.g. 01JAN2020).
- If the AE start date is missing (e.g. XXXXXXXXXX), start date will be imputed as the earlier date of: (i) the date of study drug administration, and (ii) the stop date of the AE.

The recorded/imputed dates of AEs will be used for decision whether the event is TEAE.

All AEs recorded will be presented in a data listing. Listings for AEs will include the following information: SOC, PT and Verbatim term; start and stop date/time; Time to Occurrence (for TEAE) [calculated as (AE start date – date of study drug administration +1)]; AE Duration [calculated as (AE stop date – AE start date +1)]; TEAE flag; intensity (CTCAE Grade 1 to 5); outcome (recovered/resolved, recovering/resolving, recovered/resolved with sequelae: type of sequelae, not recovered/not resolved, fatal, unknown); type of sequelae (if recovered/resolved with sequelae); relationship with study drug (unrelated, possible, probable, definite); action taken with study drug (dose not changed, drug interrupted, drug withdrawn, not applicable); any treatment received (no, medication, non-medication treatment: specify, both medication and non-medication treatment: specify the non-medication treatment); whether the event was serious (no, yes); whether the AE is classified as an infusion related reactions (IRR) including hypersensitivity and anaphylactic reaction (no, yes).

In summaries, AEs will be considered to be related if the relationship is possible, probable, or definite. If relationship or intensity is missing, it will be summarized separately under a missing category.

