#### **3.4.1 Screening Period (Day -7 to Day 1)**

Patients will sign and date the informed consent form (ICF) and undergo procedures to determine eligibility. During the Screening Period, retest for Screening is permitted only once by the Investigator's judgement. If the repeated test result is again not suitable or indeterminate for inclusion, the patient will be screen failed. Only one retest for reverse transcription polymerase chain reaction (RT-PCR) will be allowed, if study drug can be administered no more than 7 days from onset of symptom based on the retest results. And, if there is available RT-PCR result confirming SARS-CoV-2 infection prior to obtaining written informed consent (but no more than 7 days from the onset of symptoms), the result can be allowed.

If Screening visit date and the administration of study drug date (Day 1) are same, all assessments scheduled for the Screening and Day 1 visit can be performed only once on the date before randomization.

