#### **6.1.1 Adverse Events**

##### **6.1.1.1 Definition of Adverse Events**

An adverse event (AE) is defined as any untoward medical occurrence in any patient during the study which does not necessarily have a causal relationship with the study drug. Any new condition noted at Screening would be regarded as an AE, but not a TEAE.

Adverse events requiring therapy must be treated with recognized standards of medical care to protect the health and well-being of the patient. Treatment due to an AE will be recorded.

A treatment-emergent AE (TEAE) includes any untoward medical occurrence in a patient after administration of a study drug, which does not necessarily have to have a causal relationship with this the study drug. A TEAE can therefore be any unfavorable and unintended sign (including an abnormal laboratory finding), symptom, or disease temporally associated with the use of the product, whether or not related to the study drug.

Abnormal results of diagnostic procedures including laboratory test abnormalities are considered as AEs if they fulfill the following criteria:

- Result in discontinuation from the study drug

- Require treatment or any other therapeutic intervention
- Require further diagnostic evaluation (excluding a repetition of the same procedure to confirm the abnormality)
- Are clinically significant as evaluated by the Investigator

Medical intervention such as surgery, diagnostic procedures, and therapeutic procedures are not AEs, but the action taken to treat the medical condition. They should be recorded as treatment(s) of the AEs. The event term of primary cause should be recorded and reported instead of the term of surgery, diagnostic procedure, or therapeutic procedure.

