#### **6.1.1.1.6 Reporting Adverse Events**

All AEs reported or observed during the study will be recorded on the AE page in the eCRF and source documents. Information to be collected includes drug treatment, action taken with study drug, event term, date/time of onset and end date, Investigator-specified assessment of severity and relationship to study drug, seriousness of AE, any required treatment or evaluations, and outcome.

Adverse events resulting from concurrent illness, reactions to concurrent illnesses, or reactions to concurrent medications must also be reported from the date patients signs the ICF until EOT visit. Adverse events will be graded for severity according to the [Common Terminology Criteria for Adverse Events \(CTCAE\) Version 5.0](#). The Medical Dictionary for Regulatory Activities will be used to code all AEs.

Any medical condition that is present at the time that the patient is screened but does not deteriorate should not be reported as an AE. However, if it deteriorates at any time during the study, it should be recorded as an AE.

The Investigator's assessment of an AE's relationship to study drug is part of the documentation process, but it is not a factor in determining what is or is not reported in the study. If there is any doubt as to whether a clinical observation is an AE, the event will be reported.

The severity and the relationship or association of the study drug in causing or contributing to the AE will be characterized as defined in [Section 6.1.1.2](#) and [Section 6.1.1.3](#), respectively.

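### The SAP's treatment-emergence rule uses AE dates without times, so an AE arising before the infusion on Day 1 would be flagged as a TEAE if the rule is programmed as written

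*SAP*

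**What the plan says.** SAP 12.1 defines the concept by sequence: "A TEAE includes any untoward medical occurrence in a patient after administration of a study drug". Like Protocol 6.1.1.1, it sets pre-treatment findings apart: "Any new condition noted at Screening would be regarded as an AE, but not a TEAE". After the rules for completing partial dates, it gives the working instruction: "The recorded/imputed dates of AEs will be used for decision whether the event is TEAE".

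Three features of SAP 12.1 bear on how that instruction would be programmed:

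- It gives no rule for an AE whose date equals the dosing date.
- A start date that is wholly missing, or incomplete but in the month or year of dosing, is set to the earlier of the dosing date and the AE stop date. No time is imputed.
- Time to Occurrence for a TEAE is AE start date minus dosing date plus 1, so it equals 1 on the dosing day.

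The information needed for a finer rule exists. Protocol 6.1.1.1.6 collects "date/time of onset and end date" for each AE, and Protocol 5.6 has the date and time of dosing documented. The SAP's AE listing shows "SOC, PT and Verbatim term; start and stop date/time", with the TEAE flag in the same listing.

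On Day 1, footnote 6 of Protocol Table 11-1 places the physical examination, laboratory tests, vital signs, ECG and the infection signs-and-symptoms assessment before dosing. Protocol 3.4.1 also provides for the case "If Screening visit date and the administration of study drug date (Day 1) are same".

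**The concern.** The definition turns on whether an event came before or after the infusion. A calendar date cannot show that for the one day on which both are possible. Where the SAP wants clock time it says so: SAP 9 uses date and time for the duration of viral shedding and for viral AUC, and SAP 10.1 does so for time to recovery. The TEAE sentence does not, so a programmer working from the text would compare dates.

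The result would also disagree with SAP 5.5, which makes the last value before dosing the baseline. An abnormal pre-dose Day 1 laboratory result would be baseline in the laboratory tables. If it was also reported as an AE dated Day 1, it would be treatment-emergent in the AE tables.

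TEAEs, TESAEs and TEAESIs are primary endpoints (Protocol 2.2.1) and are tabulated in the first CSR (SAP Appendix 5). In groups of five and three, one wrong flag is visible in the table.

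**Working it through.** The plan states no figure that depends on this rule. The only related number is the sample size, which agrees: 3 cohorts × (5 + 1) = 18, giving 5 patients per CT-P59 dose and 3 in pooled placebo (SAP 5.2 and 5.4).

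**Step 1. Apply each possible rule to example events.** Take a dose at 10:00 on Day 1. The times are illustrative.

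| Event | AE date ≥ dose date | AE date > dose date | AE date/time ≥ dose date/time | Time to Occurrence |
|---|---|---|---|---|
| Evening before dosing | not TEAE | not TEAE | not TEAE | 0 |
| Day 1, 08:30 (pre-dose) | **TEAE** | not TEAE | not TEAE | 1 |
| Day 1, 10:40 (during infusion) | TEAE | **not TEAE** | TEAE | 1 |
| Day 2, 09:00 | TEAE | TEAE | TEAE | 2 |

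On dates alone, the two Day 1 events always share a flag, so one of them is wrong whichever operator is chosen (bold). With date and time, both are right.

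**Step 2. Which date reading does the SAP suggest?** Time to Occurrence is defined for TEAEs and takes the value 1 on the dosing day. Unknown onsets are moved to the dosing date unless the event stopped earlier. Both fit the ≥ reading, though neither states it. The likely error is therefore a pre-dose event counted as a TEAE.

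**Step 3. Who is exposed?** Only a patient with a new or deteriorated condition before the infusion on Day 1 that qualifies as an AE. Several provisions narrow this:

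- A condition present at screening that does not worsen is not an AE (Protocol 6.1.1.1.6).
- An abnormal test result is an AE only if it leads to discontinuation, treatment or further work-up, or is clinically significant (Protocol 6.1.1.1).
- Symptoms recorded in the diary are not reported as AEs (Protocol 6.3.1).
- Investigator-assessed infection signs and symptoms become AEs at the investigator's discretion (Protocol 6.1.13).

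Exposure is not removed. Screening can precede Day 1 by up to 7 days, and deterioration must be recorded as an AE.

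**Step 4. Size.** One wrongly flagged patient with no other TEAE changes incidence by 100/n points:

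- CT-P59 dose group: 100/5 = 20.0
- Pooled placebo: 100/3 = 33.3

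The documents give no rate of new pre-dose Day 1 AEs. For assumed per-patient rates p, the chance of at least one among 18 patients is 1 − (1 − p)^18:

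| Assumed p | Chance of at least one in 18 |
|---|---|
| 2% | 1 − 0.98^18 = 0.31 |
| 5% | 1 − 0.95^18 = 0.60 |
| 10% | 1 − 0.90^18 = 0.85 |

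These show sensitivity to the assumption and are not predictions.

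**The case against.** The best defence is that the sentence closes a block on partial dates. Its purpose may be only to say that imputed dates count as well as recorded ones. It does not exclude the use of time, and the governing definition, with its statement about Screening, still stands. A careful programmer would use the recorded times. The study is descriptive, every AE is listed with its times and its relationship to study drug, and among 18 patients a pre-dose event would be easy to spot.

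Much of this stands, and it rules out three stronger readings that a reader might infer:

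- **That pre-dose and infusion-day events cannot be told apart.** They can. Onset time and dosing time are recorded, and AE start time is listed.
- **That events are already misclassified, or that infusion-day reactions will be lost.** Neither is shown. The SAP states no same-day operator, and its other date rules point away from the reading that would drop infusion-day events.
- **That all 18 patients are at risk because all have pre-dose assessments.** An assessment is not an AE, and the limits in Step 3 apply.

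The defence does not remove the point. The only sentence that says how the flag is decided names dates, and relying on a programmer to depart from it leaves a primary-endpoint rule unstated. The separate eCRF item for infusion-related reactions (SAP 12.1.5) does not settle it either: the tables summarise treatment-emergent events of special interest, so the flag still applies, and the item does nothing for pre-dose findings.

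**Conclusion.** The point holds as a defect in the stated rule, not as a gap in data collection. Followed literally with dosing-date events counted as treatment-emergent, SAP 12.1 would flag a qualifying pre-dose Day 1 AE as a TEAE. That conflicts with its own definition and is inconsistent with the baseline rule in SAP 5.5.

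The 20-point and 33-point shifts each assume one such patient, no other TEAE in that patient, and a program that ignores the recorded times. How often this would happen cannot be derived from the documents. The correction is worth making because it is nearly free and the endpoint is primary.

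**What to change.** Replace the sentence in SAP 12.1 with a rule such as:

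> An AE is treatment-emergent if its start date/time is at or after the start date/time of study drug infusion. If the AE start date is, or is imputed to, the dosing date and the onset time is missing, the AE is classified as a TEAE unless the record shows that it was noted at Screening or ended before the infusion. For other days, recorded or imputed dates are used.

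Use the same flag for TESAEs and TEAESIs. Anchoring on the start of infusion keeps reactions during the infusion on the treatment-emergent side. The missing-time default preserves the SAP's cautious handling of unknown onsets.

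The cost is a few lines in the SAP and a small programming change using fields already collected. SAP 5 allows updates after the data review meeting and before database hard lock. The downside is that slightly fewer events may be counted as TEAEs than under a literal date rule.
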